## 1. Program Summary

Research Title	Establishment of a Rapid Detection Method for Microorganisms in the Lower Genital Tract Using MALDI-TOF MS and Its Clinical Application in Infertility
Purpose of the study	
1) Development and robustness evaluation of a rapid detection method based on Matrix-Assisted Laser Desorption/Ionization Time of Flight Mass Spectrometry (MALDI-TOF MS) for the simultaneous detection of multiple pathogens and CST in the lower genital tract
 
2) Assessment of the correlation between lower genital tract pathogenic infections, CST and infertility using the newly developed assay

Research Hypothesis	Possible correlation between CST, pathogens, and infertility in the lower genital tract
Study Design	Part I: Diagnostic tests; Part II: Case-control

Case group	Part I: MALDI-TOF MS test; Part II: Infertile individuals
Control group	Part I: Microbiological culture; Part II: Clinically proven to be spontaneous pregnancy
Sample size	Part I: 77 cases in each group; Part II: 114 cases in each group
Selection Criteria	
The first part of all test samples are acquired standards with no inclusion criteria; the second part:
 
Inclusion Criteria:
 
Case group:
 
 
1) Female aged 18-40
 
2) Regular menstrual cycle
 
2) Conform to the clinical diagnosis of infertility
 
3) No sexual life 3 days before the examination
 
 
control group:
 
 
1) Female aged 18-40
 
2) Regular menstrual cycle
 
3) Patients who did pre-pregnancy consultation in our hospital, pregnant at the time of 3-month follow-up
 
4) No sexual life 3 days before the examination
 
 
-
 
Exclusion Criteria:
 
Case group:
 
 
1) Infertility due to malformation of reproductive tract
 
2) Infertility caused by endocrine factors such as polycystic ovary syndrome, premature ovarian failure and severe hyperthyroidism
 
3) Infertility due to male factors
 
4) Patients with malignant tumors
 
5) Patients with autoimmune diseases
 
6) Patients with severe heart, kidney and other basic diseases
 
7) Patients who consumed antibiotics 3 days before the examination
 

	
8) Have the habit of smoking and drinking
 
Control group:
 
 
1) Pregnancy by various assisted reproductive means
 
2) Patients with malignant tumors
 
3) Patients with autoimmune diseases
 
4) Patients with severe heart, kidney and other basic diseases
 
5) Patients who consumed antibiotics 3 days before the examination
 
6) Have the habit of smoking and drinking
 

Exclusion Criteria
	
All samples tested in Part I were acquired standards with no inclusion criteria; Part II:
 
Case group:
 
 
1) Infertility due to malformation of reproductive tract
 
2) Infertility caused by endocrine factors such as polycystic ovary syndrome, premature ovarian failure and severe hyperthyroidism
 
3) Infertility due to male factors
 
4) Patients with malignant tumors
 
5) Patients with autoimmune diseases
 
6) Patients with severe heart, kidney and other basic diseases
 
7) Patients who consumed antibiotics 3 days before the examination
 
8) Have the habit of smoking and drinking
 
 
Control group:
 
 
1) Pregnancy by various assisted reproductive means
 
2) Patients with malignant tumors
 
3) Patients with autoimmune diseases
 
4) Patients with severe heart, kidney and other basic diseases
 
5) Patients who consumed antibiotics 3 days before the examination
 
6) Have the habit of smoking and drinking
 

Ending evaluation
	
Main indicators: microbiological test results, are recorded as negative, positive

indicators	
Safety evaluation indicators	Pain indicators: pain score; bleeding indicators: bleeding volume assessment (blood staining area method), blood routine; cervical and vaginal infection: white belt routine

## 2. Research Background

### 1. 1 Research significance

The cervical canal and vagina (collectively referred to as the lower genital tract) are important components of the female reproductive tract, and infections of the lower genital tract are also the most common gynecologic conditions. Infections such as *Neisseria gonorrhoeae* (NG), *Mycoplasma urealyticum* (UU) and *Chlamydia trachomatis* (CT) not only cause discomfort, but may also lead to infertility, ectopic pregnancy, miscarriage and premature birth. These infections not only cause uncomfortable symptoms, but also may lead to infertility, ectopic pregnancy, miscarriage, premature birth and other adverse pregnancy outcomes, which seriously affect women's physical and mental health and family harmony. The infection may lead to infertility, ectopic pregnancy, miscarriage, preterm delivery and other adverse pregnancy outcomes, which can seriously affect women's physical and mental health and family harmony. Disruption of the ecosystem of the lower genital tract can lead to overgrowth of pathogens, resulting in vaginal infections and sexually transmitted infections (STIs). The disruption of the lower reproductive tract ecosystem can lead to an overgrowth of pathogens that can cause vaginal infections and sexually transmitted infections (STIs). The community state type (CST) of cervical and vaginal colonizing bacteria is the most important component of the lower genital tract microecosystem and has an important impact on the health of the lower genital tract. It has an important impact on the health of the lower reproductive tract. Recent studies have shown that abnormal CST is strongly associated with infertility and poor pregnancy outcomes. . Therefore, rapid, accurate and cost-effective detection of common pathogens and CST in the reproductive tract is a technique that gynecologists are eager to achieve, not only to comprehensively analyze the etiology

of infertility and poor pregnancy outcomes in patients, but also to further investigate the correlation between dynamic changes in CST and various pathogenic infections and diseases in the lower reproductive tract.

Currently, although inflammatory vaginal diseases such as mycosis fungoides, bacterial vaginosis, and trichomoniasis can be detected rapidly (30-60 minutes) by simultaneous routine leukocyte or vaginal microecological evaluation. However, in order to assess the infection status of the lower genital tract, sampling, culture and testing of *Neisseria gonorrhoeae*, mycoplasma and chlamydia need to be performed separately, which takes a long time (ranging from 2-5 days) and increases the patient's pain and may lead to an increase in the false-negative rate of the later specimens due to repeated sampling, and CST analysis is costly and time-consuming due to the use of 16SrRNA and high-throughput sequencing. Currently, CST analysis is only used in scientific research and lacks practical significance for clinical diagnosis and treatment of patients.

The emerging Matrix-Assisted Laser Desorption/Ionization Time of Flight Mass Spectrometry (MALDI-TOF MS) detection system can detect multiple pathogenic microorganisms and subtypes simultaneously than traditional detection techniques such as fluorescent PCR technology, with high detection stability and accuracy, and lower cost and faster analysis than second-generation sequencing, and has been gradually used in recent years. in clinical testing The project team has previously used MALDI to detect a variety of pathogenic microorganisms. The project team has previously established a cervical fluid-based cell PAX1 methylation detection platform using MALDI-TOF MS (**Patent No. CN202010753067.8., paper submitted**), and has extensive experience in the development of MALDI-TOF MS platform for clinical testing. This study will use the MALDI-TOF MS platform to establish a combined detection system for common pathogens in the lower genital tract and CST to fill this technical gap and address the practical needs of clinicians.

## **1. 2 Current status of domestic and international research.**

Sexually transmitted infections (STIs) are a major global health problem, with

127 million and 27 million adults worldwide having *Chlamydia trachomatis* and gonococcal infections in 2012, according to statistics. . Both infections are mainly asymptomatic and curable, but if untreated or ineffective, they can lead to pelvic inflammatory disease, infertility and ectopic pregnancy, and *Chlamydia trachomatis* infection is also associated with a variety of adverse pregnancy outcomes, such as chorioamnionitis, preterm delivery and low birth weight . Reproductive mycoplasma infections are as high as 2.0%-7.3% and are thought to be associated with UTIs, cervicitis, pelvic inflammatory disease, and infertility .

The vast majority of patients with lower genital tract pathogens are only transiently infected and can be cleared by their own or pharmacological treatment, while only a minority of patients have serious adverse outcomes, suggesting that other factors influence the pathogenic evolution of these pathogens. Previous studies have shown that the type and abundance of long-term parasitic flora in the human cavity are closely related to important aspects of disease development such as immune regulation, inflammatory response, cytogenetic mutation, angiogenesis, and tissue remodeling. . Therefore, in recent years, microecology has received a lot of attention from many fields such as immunity and metabolism. Since the discovery of *Lactobacillus vaginalis* by Albert Doderlein in 1982, a number of studies have been conducted to demonstrate that a decrease in the absence of *Lactobacillus vaginalis* is a major cause of inflammatory vaginal diseases such as mycobacteria and bacterial vaginitis. However, because early studies on genital tract pathogens were mainly performed by microbiological microscopy, staining, and culture, it was not possible to subtype *Lactobacillus*, and the correlation between lower genital tract CST and obstetrical and gynecological diseases has only recently been emphasized. Recently, many scholars have studied the relationship between vaginal CST and obstetric and gynecological diseases, and such studies have suggested that abnormal CST in the lower genital tract can lead to pelvic inflammatory disease infertility and adverse pregnancy outcomes. However, does abnormal CST promote gonorrhea? However, it is unclear whether CST abnormalities promote infection and persistence of infertility-causing pathogens such as *Neisseria gonorrhoeae*, *Mycoplasma*

urealyticum and Chlamydia trachomatis.

Currently, most clinical tests for *Neisseria gonorrhoeae*, mycoplasma and chlamydia are performed using microbial cultures, and vaginal CST analysis is performed using 16SrRNA or macrogenomic sequencing. . Therefore, performing multiple analyses on a patient at the same time is not only expensive, but also requires multiple sampling, which affects the accuracy of the results and makes it difficult to be widely implemented in the clinic. To the best of our knowledge, there is no accurate and cost-effective method for simultaneous detection of common pathogenic microorganisms in the lower genital tract. Therefore, this study proposes to establish a combined detection system for common pathogens and CST in the lower genital tract based on the MALDI-TOF MS testing platform, which will enable clinicians to accurately detect pathogens and common microorganisms in the lower genital tract with a single sample at a reasonable testing cost, and provide more accurate information and evidence for patient disease status assessment and treatment guidance. In addition, the project team will evaluate and compare the lower genital tract microecology of infertile and healthy control women using the constructed assay, and initially explore the correlation between lower genital tract microecology and infertility, and the correlation between various pathogenic infections and lower genital tract CST.

### **3. Purpose of the study**

1) Development and robustness of a rapid detection method for microorganisms in the lower genital tract based on time-of-flight mass spectrometry (MALDI-TOF MS) for simultaneous detection of multiple pathogens and CST

2) Assessment of the association between lower genital tract pathogenic infections, CST and infertility using a newly developed assay

### **4. Study design**

The first part of this study is a diagnostic test using using a standard pathogenic strain; the second part is a prospective case-control study

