## **6. estimation of sample size and grouping method**

### 6.1 Estimation of sample size

#### 6.1.1 Part I: Comparison of sensitivity of dose information between the two groups

Single and mixed standard bacterial solutions and blank controls were 11 in total, so the chance of the appearance of four microorganisms in various standard strain solutions was 0.18, and different studies showed that the culture sensitivity of gonococci, lactobacilli, mycoplasma, and chlamydia was 40-60% and specificity 95-98%; time-of-flight mass spectrometry detection was >99% in different studies, and the parameters were brought into

PASS according to  $\alpha=0.1$  Software calculation path: Tests for Two Independent Sensitivities,  $N=44-72$ , taking the least integer multiple of 11 for  $>72$ , i.e., 77 cases in each group

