### 8. Research steps

#### **8.1 Part I. Development of a rapid detection method based on MALDI-TOF MS for simultaneous detection of multiple pathogens and CST in the lower genital tract and evaluation of diagnostic efficacy**

8.1.1 Find the relatively conserved regions of virulence factor sequences of each pathogen according to the database, intercept the specific sequences from the conserved regions of each pathogen to design multiplex PCR amplification primers and single base extension (SBE) primers for each strain to construct MALDI-TOF MS assays.

8.1.2 Purchase standard pathogen strains, culture standard concentrations (i.e., high concentrations) of standard pathogens using the culture method to identify standard pathogens and their activities

8.1.3 Formulation of single, mixed and negative control standards with standard pathogens.

8.1.4 Gold standard: The actual pathogen type added to the standard is the gold standard.

8.1.5 Detection of standards at gradient dilution concentrations by incubation method and MALDI-TOF MS, respectively.

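### Part I gives no information on strain coverage, so its sensitivity, and the difference from culture, apply only to the purchased strains tested

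*Combined protocol and SAP*

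**What the plan says.** Section 4 describes Part I in the singular: "The first part of this study is a diagnostic test using using a standard pathogenic strain". Step 8.1.2 uses the plural, "Purchase standard pathogen strains", and no section gives the number of strains per organism.

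The assay is sequence-based. Step 8.1.1 is to "Find the relatively conserved regions of virulence factor sequences of each pathogen according to the database" and then to "design multiplex PCR amplification primers and single base extension (SBE) primers for each strain to construct MALDI-TOF MS assays". Under 8.1.2 the standards are grown and identified by culture before use. In 8.1.4 the reference is the organism put in: "The actual pathogen type added to the standard is the gold standard". What varies is composition (single, mixed or negative, 8.1.3) and concentration: "Detection of standards at gradient dilution concentrations by incubation method and MALDI-TOF MS, respectively".

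Section 6.1.1 counts 11 solutions for four microorganisms, puts each organism in a share of 0.18 of them, obtains N = 44 to 72 and settles on 77 per group by "taking the least integer multiple of 11". Section 12 plans sensitivity, specificity and predictive values for Part I only. Sections 1 and 3 name robustness of the method as part of the purpose. Part II (8.2) then applies the assay to patient swabs.

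**The concern.** A primer-based assay can miss a strain whose sequence differs at a primer or extension site. Repeats and dilutions of a strain that does match cannot reveal this, however many are run. Culture does not depend on those sites, so this failure belongs to the new method alone, and the panel as described would not show it.

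At stake is what Part I may claim. A sensitivity measured on a few purchased strains could be read as the assay's diagnostic sensitivity. In Part II a woman carrying an unmatched strain would be recorded as negative, and no planned analysis separates that from absence of infection.

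**Working it through.** **Inputs from section 6.1.1.** Culture sensitivity 0.40 to 0.60; MALDI-TOF MS above 0.99 (0.99 used here); α = 0.1; share positive 0.18, which is 2/11; 77 tests per group. Sidedness and power are not stated.

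**The plan's own figure.** Assume a two-sided test and 90% power, with a pooled z-test of two independent sensitivities and power by exact binomial enumeration.
- Culture 0.40: 8 positives needed; 8/0.18 = 44.4.
- Culture 0.60: 13 positives needed; 13/0.18 = 72.2.

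This matches 44 to 72, and the next multiple of 11 is 77. The sample size reproduces under these assumptions, so the point is not an arithmetic error.

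**What 77 tests say about one strain.** Positives per organism: 77 × 2/11 = 14. If all 14 are detected, the two-sided 95% lower limit is 0.025^(1/14) = 0.77. This treats the 14 tests as equal repeats, which the dilutions in 8.1.5 make only approximate.

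**What they say about strain coverage.** The unit is now the strain. If k of k strains are detected, the one-sided 95% lower bound on the share of strains covered is 0.05^(1/k):

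| Strains, all detected | Lower bound on coverage |
|---|---|
| 1 | 5% |
| 3 | 37% |
| 5 | 55% |
| 7 | 65% |

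These bounds treat the strains as a random sample of circulating strains. Purchased reference strains are not that, so the bounds show how little a few strains can establish; they do not estimate coverage.

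**What imperfect coverage would do.** The documents give no coverage figure. Assume a share c of circulating strains is detectable and culture is unchanged. The lead over culture is 0.99c minus 0.60 to 0.40:

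| c (assumed) | 0.99c | Lead over culture, points |
|---|---|---|
| 1.00 | 0.990 | 39 to 59 |
| 0.95 | 0.941 | 34 to 54 |
| 0.90 | 0.891 | 29 to 49 |
| 0.80 | 0.792 | 19 to 39 |

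Part I on one matched strain would look the same in every row.

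**What a few more strains can reveal.** The chance that every strain passes despite mismatch is c^k. At 10% mismatch it is 0.9^3 = 73% for three strains and 0.9^7 = 48% for seven. At 20% it is 0.8^3 = 51% and 0.8^7 = 21%. A small panel can expose gross drop-out but cannot rule out mismatch of 10% to 20%.

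**The case against.** The strongest reply is that the plan already addresses coverage: 8.1.1 searches a database for conserved regions before primers are designed, and if the targets are fully conserved nothing is lost. That stands as mitigation. It does not stand as evidence, because no result of the search is to be reported and no test follows from it.

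A reader might infer that the advantage over culture is overstated. The documents do not support that. Primer mismatch affects only the sequence-based method, but 8.1.2 puts forward standards already grown and identified by culture: "Purchase standard pathogen strains, culture standard concentrations (i.e., high concentrations) of standard pathogens using the culture method to identify standard pathogens and their activities". This also limits the panel to strains that culture can detect, which may favour culture. The two effects pull in opposite directions and neither can be sized from the documents.

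A reader might also infer that exactly one strain per organism is used. The singular in section 4 and the 11 solutions for four microorganisms make that likely, but 8.1.2 says strains, the make-up of the 11 solutions is not given, and the number per organism is not stated.

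Nor do the documents say that Part I accuracy will be used to correct Part II, or claim superiority over culture in patients. A loss of Part II power is possible but cannot be calculated without a coverage figure. Finally, drop-out need not stay hidden in patients: 10.1 records clinical-report results and 10.2 the MALDI-TOF MS results. The data for a partial check would therefore exist, but neither 8.2 nor section 12 plans the comparison.

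**Conclusion.** The point holds as a limit on what Part I can conclude. As written, Part I carries no information on strain coverage, although robustness is a stated purpose, and its sensitivity and difference from culture apply only to the strains tested. On the likely reading of one strain per organism, 14 of 14 detections support at least 77% for that strain and only 5% as a bound on coverage. Over an assumed mismatch of 0% to 20%, the loss in the planned lead ranges from nothing to about 20 points. The direction of any net bias against culture is unknown. The sample size of 77 is not in question here.

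**What to change.** 1. State the number of strains per organism. At 8.1.1, check every PCR and extension primer site against all sequences of the species in the database already used, and report the share matched per organism. This is the most informative step on coverage and needs no laboratory work.
2. Keep 77 tests per group. Where more than one reference strain can be bought, spread the tests over several strains, balanced across the dilution levels of 8.1.5 so that strain and concentration are not confounded. Report detection per strain as well as per organism, and say that a few strains cannot exclude 10% to 20% mismatch.
3. Report Part I as analytical sensitivity for the strains tested, and draw no claim of superiority over culture in patients from it.
4. Add to section 12 a cross-tabulation of the clinical-report results (10.1) against the MALDI-TOF MS results (10.2). Women positive on the clinical report and negative on the assay are where drop-out could show. The check is partial: the clinical tests are imperfect and there may be few positives.

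The cost is a few more reference strains, one database check, fewer repeats of any single strain and a narrower Part I claim. The number of assays does not change.

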### **5. Case selection**

#### 5.1 Entry Criteria

1. Subjects voluntarily enrolled in the study and signed an informed consent form
2. The inclusion criteria for the case and control groups were as follows.

#### **Case group:**

- 1) Female aged 18-40
- 2) Regular menstrual cycle
- 2) Conform to the clinical diagnosis of infertility
- 3) No sexual life 3 days before the examination

#### **control group:**

- 1) Female aged 18-40
- 2) Regular menstrual cycle
- 3) Patients who did pre-pregnancy consultation in our hospital, pregnant at the time of 3-month follow-up
- 4) No sexual life 3 days before the examination

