#### **5.2 Exclusion criteria.**

##### Case group:

- 1) Infertility due to malformation of reproductive tract
- 2) Infertility caused by endocrine factors such as polycystic ovary syndrome,

premature ovarian failure and severe hyperthyroidism

- 3) Infertility due to male factors
- 4) Patients with malignant tumors
- 5) Patients with autoimmune diseases
- 6) Patients with severe heart, kidney and other basic diseases
- 7) Patients who consumed antibiotics 3 days before the examination
- 8) Have the habit of smoking and drinking

Control group:

- 1) Pregnancy by various assisted reproductive means
- 2) Patients with malignant tumors
- 3) Patients with autoimmune diseases
- 4) Patients with severe heart, kidney and other basic diseases
- 5) Patients who consumed antibiotics 3 days before the examination
- 6) Have the habit of smoking and drinking

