### **5.3 Exit Criteria**

**Case group.**

- 1) Unsatisfactory sample nucleic acid extraction
- 2) Intraoperative detection of developmental malformations or other non-colony related factors that can clearly cause infertility

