**Control group.**

- 1) Unsatisfactory sample nucleic acid extraction
- 2) No spontaneous pregnancy at the time of follow-up

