#### 6.2 Grouping method

Case group were patients with clinical diagnosis of infertility: sexually active, uncontraceptive and infertile for 2 years

The control group was those with spontaneous pregnancy: those with spontaneous pregnancy at the follow-up visit 3 months after consultation

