10.2 MALDI-TOF MS test results were recorded as: microbial type, positive, negative

## 11. Security evaluation

This study involves only 1 vaginal and cervical secretion collection, which is consistent with HPV sampling during cervical screening in routine clinical testing and does not cause additional collection points or additional consultation costs, and is safe. It may cause pain and a little bleeding to the patient, neither of which will have any impact on the patient's health. Inform the patient before the operation to avoid causing panic. If the patient has intercourse immediately after the test or performs inappropriate transvaginal operations that may lead to infection, the patient is advised to avoid intercourse, sitz baths and other transvaginal operations without professional medical guidance for 3 days after sampling.

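### The Part II case and control definitions are not mutually exclusive: a woman who meets the 2-year infertility definition at consultation and then conceives spontaneously within 3 months satisfies both

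*Combined protocol and SAP*

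**What the plan says.** **Cases.** Section 5.1 requires that a case "Conform to the clinical diagnosis of infertility", and 6.2 spells this out as "sexually active, uncontraceptive and infertile for 2 years". Section 5.2 removes infertility due to malformation, endocrine causes or male factors. Section 5.3 removes a case for failed nucleic acid extraction or for "Intraoperative detection of developmental malformations or other non-colony related factors that can clearly cause infertility". Conceiving later is not an exit reason.

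**Controls.** Section 5.1 asks for "Patients who did pre-pregnancy consultation in our hospital, pregnant at the time of 3-month follow-up", together with age 18-40, a regular cycle and 3 days' abstinence. Section 6.2 describes the group as "those with spontaneous pregnancy at the follow-up visit 3 months after consultation". The only exclusion in 5.2 that bears on fertility is "Pregnancy by various assisted reproductive means"; the others concern general health, antibiotics, and smoking and drinking. Section 5.3 removes a control for failed extraction or for "No spontaneous pregnancy at the time of follow-up".

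**Sampling and data.** Section 11 states: "This study involves only 1 vaginal and cervical secretion collection". Section 8.2.2 lists duration of infertility among the possible confounders to be collected, but no eligibility rule uses it. The background (1.2) describes the intended contrast as infertile women against healthy controls.

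**The concern.** Case status depends on time already spent trying. Control status depends on what happens in the 3 months after a clinic visit, whatever came before. The 3 months run from the consultation, not from the start of trying, so they do not by themselves separate the two groups.

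Two things are at stake. First, women who are infertile by the plan's own definition can enter the comparison group. If their pathogen or CST status resembles that of cases, the Part II association is diluted. Second, because control status is settled only at follow-up and no rule takes precedence, such a woman could be placed in either group after the event.

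**Working it through.** **Step 1: can one woman satisfy both definitions?** Take a woman aged 18-40 with a regular cycle who has had 2 years of unprotected intercourse without pregnancy, has no excluded cause and no other listed exclusion, and attends a pre-pregnancy consultation.

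| Rule | As a case | As a control, if she conceives spontaneously within 3 months |
|---|---|---|
| 5.1 inclusion | met, with the diagnosis as defined in 6.2 | met |
| 5.2 exclusion | none applies | none applies |
| 5.3 exit | none applies; conception is not listed | none applies; she is pregnant |
| 6.2 grouping | met at the consultation | met at follow-up |

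No section assigns her to one group. A woman with less than 2 years of trying is not a case under 6.2 and can be a control, so she creates no overlap.

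**Step 2: swab timing.** The overlap at sampling requires the control swab to precede pregnancy. The plan has one collection per woman (section 11) and an exit rule for controls found not pregnant at follow-up (5.3). Entry therefore comes before the outcome, and a swab at the consultation is the natural reading. It is an inference; no section states it.

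**Step 3: how many controls could be affected?** The documents do not give the share, so this step is an illustration on assumed figures. Let w be the share of long-trying women among those consulting. Assume monthly conception of 20% in ordinary women and 2% to 5% in long-trying women. Conception within 3 months is 1 − (1 − m)³:

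- ordinary: 1 − 0.80³ = 0.488
- long-trying: 1 − 0.98³ = 0.0588 to 1 − 0.95³ = 0.1426

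The share among controls is f = w·c / (w·c + (1 − w)·0.488), where c is the 3-month figure for long-trying women.

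- w = 10%: f = 0.00588 / (0.00588 + 0.4392) = 1.3%, up to 0.01426 / (0.01426 + 0.4392) = 3.1%
- w = 30%: f = 0.01764 / (0.01764 + 0.3416) = 4.9%, up to 0.04279 / (0.04279 + 0.3416) = 11.1%

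**Step 4: effect on the odds ratio.** Assume exposure of 35% in infertile and 20% in fertile women, and fully case-like exposure in the affected controls. Then OR = odds(0.35) / odds(0.20 + 0.15f).

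| f | Exposure in controls | Expected OR |
|---|---|---|
| 0 | 20.0% | 2.15 |
| 1.3% | 20.2% | 2.13 |
| 3.1% | 20.5% | 2.09 |
| 4.9% | 20.7% | 2.06 |
| 11.1% | 21.7% | 1.95 |

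On the difference scale the contrast shrinks by the factor (1 − f), whatever the exposure rates.

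**Step 5: larger shares.** With f = 10%, 20% or 30%, the same formula gives 1.97, 1.80 or 1.66. Under the conception rates in step 3, f = 30% needs w/(1 − w) = 0.3 × 0.488 / (0.7c). That is 1.47 at c = 0.1426 and 3.56 at c = 0.0588, so about 59% to 78% of those consulting would have to be long-trying. If affected controls carry exposure halfway between the groups (27.5%), the three odds ratios become 2.06, 1.97 and 1.88.

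**The case against.** Four points can be made for the plan as written.

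- **Different entry routes.** Controls come from pre-pregnancy consultation. Section 6.1.2 describes infertility patients as women attending for infertility, and the intraoperative exit rule in 5.3 suggests that at least some cases have an operative work-up. Two years of trying is also not the whole case rule, because the cause exclusions apply. This stands as a reason to expect little overlap, but it is not a written exclusion.
- **Conception selects against long-trying women.** They must conceive spontaneously within 3 months to remain controls, and those who do may carry less of any exposure that impairs conception. This stands, and it is why the effect is probably small.
- **Collected data may help.** Section 8.2.2 records duration of infertility, and section 12 plans stratified analysis and logistic regression. Overlap could be detected if controls complete the same item, which the plan does not make explicit.
- **An overly strict control definition has its own cost.** Excluding any woman who was ever infertile would filter the controls' history with no matching restriction on cases, and could inflate the association. This stands against going beyond the minimum change.

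A reader might also infer more than the documents support:

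- *That many controls will be subfertile because women with difficulty conceiving seek such consultations.* No section says who attends, and the 10% to 30% shares with fully case-like exposure are closer to an upper bound.
- *That the rates in 6.1.2 show severe bias.* Taken literally (0.01% and 0.46%), they give an odds ratio falling from 46.2 to 8.4 at f = 10%. But the difference falls only from 0.45 to 0.405 percentage points, and 114 women per group would yield 114 × 0.0001 = 0.01 and 114 × 0.0046 = 0.52 expected positives, too few to estimate any odds ratio. The fall reflects a near-zero control rate, not a large share of misplaced women.

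**Conclusion.** The point holds as a defect in the written rules. The two Part II definitions overlap, and the plan does not say which group a woman in the overlap belongs to. This rests on the eligibility, exit and grouping text and on one inference, that the control swab is taken before pregnancy.

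The expected consequence is dilution of the association, of unknown and probably small size. On the assumed 35% and 20% exposures and 1.3% to 11.1% of controls affected, an odds ratio of 2.15 becomes about 2.13 to 1.95. Those exposures, the conception rates and the share of long-trying women are all assumptions. The relative fall in the odds ratio would be larger if exposure in fertile women were very rare.

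The documents do not support saying that the comparison is invalid, or that women who had been trying for 12 to 23 months are misclassified: under the plan's 2-year definition they are not cases. The change is worth making because a case-control comparison needs exclusive groups and this one can be had cheaply.

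**What to change.** 1. Add to the control exclusions in 5.2, and in the program summary: *meets the case definition in 6.2 at the time of sampling*.
2. In the 8.2.2 form, record time trying before the consultation for controls as well as cases.
3. State in 6.2 that group is fixed by history at sampling: a woman who meets the case definition then is never a control, even if she later conceives.
4. State in 8.2.3 when the control swab is taken, since items 1 and 3 work as intended only if it precedes pregnancy.

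The cost is one exclusion line, one question and two clarifying sentences, and a few otherwise eligible controls are lost. Women with less than 2 years of trying can be handled by a sensitivity analysis according to the controls' time trying. A 12-month limit or an exclusion for any past infertility is optional and is not needed to make the groups exclusive.
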